## 6.10 Blood Samples for Pharmacokinetics

Pharmacokinetic samples will be drawn on all patients randomized in the trial. Capillary blood samples will be drawn by heel stick with a goal volume of 0.4 ml blood into a lithium heparin tube. An outline of a sampling schedule is listed below. In light of the sparse sampling regimen, some allowance for variation from this schedule is anticipated to reflect feeding and sleeping schedules for the child. Wherever possible, pharmacokinetic samples will be paired with a standard of care blood draw. A description of blood processing is outlined in Appendix 3. Where possible, blood draws would be 2 or 3 samples after an individual dose.

One or two samples collected for pharmacokinetic analysis may be retained to examine ethanol pharmacokinetics for infants on maximum dose buprenorphine and phenobarbital. This will help establish the total ethanol exposure following buprenorphine administration, and differentiate from ethyl and non-ethyl alcohol generated by normal metabolic processes in non-ethanol exposed infants.

**Table 9: Schedule of Pharmacokinetic Blood Draws**

Week 1	Peak within 24 hours of initiation of therapy
	Peak and trough surrounding single dose x 2
	Single mid-interval dose
Weeks 2 onward	Peak and trough surrounding single dose
	Single mid-interval dose
Dose Cessation	Single sample between 12-24 hours after final dose
Periods of Co-administration of phenobarbital	Peak and trough surrounding single dose every three days

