## **2 STUDY OBJECTIVES**

### **2.1 Primary Objective**

To define buprenorphine pharmacokinetic exposure in infants treated with buprenorphine for neonatal abstinence syndrome (NAS) using a model-based optimized dose.

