## 4 STUDY POPULATION

### 4.1 Inclusion Criteria

Patients eligible for participation include:

1.  $\geq$  36 weeks gestation
2. Exposure to opioids in utero
3. Demonstration of signs and symptoms of neonatal abstinence syndrome requiring treatment

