## 6.9 Study Data

The following elements will be collected in the study data base:

- mode of birth
- gestational age
- gender
- Apgar scores
- NAS scores
- birth weight
- daily weight
- daily intake (cc/kg/day) and type of feed
- stool number and characteristics
- head circumference
- concomitant medication
- urine drug screen results
- dates and times of primary treatment and phenobarbital (if applicable)
- medical record number
- adverse events
- respiratory patterns

Maternal elements to be collected include:

- opioid (methadone, buprenorphine, or other) dose
- urine drug screen
- tobacco use (none,  $\leq 5$  cigarettes/day,  $> 5$  cigarettes/day)
- concomitant medication during gestation
- medical record number
- date of birth

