## 6.14 Blood Samples for Pharmacogenomics

A single 0.2-0.4 ml whole blood sample is collected in a lithium heparin tube. This sample will be collected prior to the initiation of therapy. If this is not possible, the sample can be collected at any time post randomization. Wherever possible, pharmacogenetic samples will be paired with a standard of care blood draw. A description of blood processing is outlined in Appendix 3. Alternatively, DNA can be obtained through the use of a cheek swab.

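### Table 9 has no PK sample before the first dose although infants of mothers on buprenorphine can enrol, so residual maternal drug cannot be measured and may inflate early exposure in those infants

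*Protocol*

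**What the plan says.** **Objective.** Protocol section 2.1 states the primary objective as "To define buprenorphine pharmacokinetic exposure in infants treated with buprenorphine for neonatal abstinence syndrome (NAS) using a model-based optimized dose". Section 3.2.1 compares the exposure profile from the population model with the model simulations.

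**Who can enrol.** Section 4.1 asks for "Exposure to opioids in utero" without naming the opioid. None of the five exclusions in section 4.2 concerns maternal buprenorphine. Section 6.9 lists "opioid (methadone, buprenorphine, or other) dose" among the maternal data, so such mothers are expected.

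**When blood is drawn.** Section 6.10 introduces the schedule with "An outline of a sampling schedule is listed below" and allows variation for feeding and sleeping. Table 9 opens with "Peak within 24 hours of initiation of therapy" and adds "Peak and trough surrounding single dose x 2" and one mid-interval sample in week 1. Later rows are peak and trough pairs, mid-interval samples, one sample after cessation, and pairs during phenobarbital co-administration. None comes before the first dose.

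**The only blood sample planned before treatment** is the pharmacogenetic one in section 6.14: "This sample will be collected prior to the initiation of therapy". It is 0.2 to 0.4 mL in lithium heparin, is not listed for drug assay, and may be taken later or replaced by a cheek swab.

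**Analysis.** Section 7.1 specifies a nonlinear mixed-effects model using the parent-metabolite relationship. It does not say how drug already present at the first dose is handled.

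**The concern.** The trial gives a drug that some infants may already carry from the mother, and measures that same drug and its metabolite without a baseline. In such an infant an early concentration is the sum of study drug and residue, and no scheduled sample separates the two.

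The likely direction is upward for early exposure and downward for apparent clearance. As the residue washes out, apparent clearance would seem to rise with age. That could be mistaken for maturation, and section 7.1 plans to evaluate developmental change. Residual norbuprenorphine would disturb the parent-metabolite relationship in the same way.

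The early period matters here. Section 1.3.4.1 ties time to stabilization to average concentration up to that time. Table 4 puts simulated stabilization for the chosen initial dose and titration rate at 131.5 h, which falls inside week 1. Week 1 also has six scheduled draws, against three in each later week unless phenobarbital is given.

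A sampling schedule belongs in the protocol, and no analysis plan can recover a sample that was never drawn.

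**Working it through.** The protocol states no figure for residual maternal drug, so there is nothing to reproduce. The calculation below shows what size is possible.

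**Inputs from the protocol**
- Mean of quantifiable concentrations in the earlier trial (BBORN): 0.5 ng/mL (section 1.3.4.4). It is used here as the average concentration from study drug.
- Week-1 draws: 1 + 2 × 2 + 1 = 6 (Table 9).
- Blood limit: 12 mL (section 8.1).

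**Assumptions, not in the protocol**
- Residual at first dose, C0: 0.05 to 0.4 ng/mL.
- Half-life, t½: 12 to 36 h, first-order decline, k = ln 2 / t½.

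**Share of the concentration at 24 h**, the end of the window for the first draw: C0·e^(−24k) / (C0·e^(−24k) + 0.5).
- Low: 0.05 × 0.25 = 0.0125; 0.0125 / 0.5125 = 2.4%.
- High: 0.4 × 0.63 = 0.252; 0.252 / 0.752 = 33.5%.

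**Share of week-1 AUC**: residual AUC = C0·(1 − e^(−168k)) / k; study-drug AUC = 0.5 × 168 = 84 ng·h/mL.
- Low: residual AUC 0.87; 0.87 / 84.87 = 1.0%.
- High: residual AUC 19.96; 19.96 / 103.96 = 19.2%.

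**Share of the concentration at 168 h**
- Low: effectively zero.
- High: 0.4 × 0.0394 = 0.0157 ng/mL; 0.0157 / 0.5157 = 3.1%.

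**Sensitivity to the reference level.** The 0.5 ng/mL arose under an initial dose of 5.3 mcg/kg; this trial starts at 8 mcg/kg (Table 3). Linear scaling, a further assumption, gives 0.5 × 8 / 5.3 = 0.755 ng/mL. The ranges become 1.6% to 25% at 24 h and 0.7% to 13.6% of week-1 AUC.

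**Blood budget**
- The Table 10 rows sum to 0.8 + 0.4 + 0.4 + 8.0 = 9.6 mL for a girl and 9.8 mL for a boy with circumcision. The printed totals are 10.6 and 10.8 mL, 1.0 mL more than the rows.
- One more 0.4 mL draw gives 10.0 and 10.2 mL on the row sums, or 11.0 and 11.2 mL on the printed totals. All are below 12 mL.

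**The case against.** The strongest reply is that the gap may have little effect. Section 6.9 lists buprenorphine only as one value of a data field, so the number of affected infants could be zero. Age at first dose is not given either. Maternal opioid dose and the infant and maternal urine drug screens are recorded, so affected infants can be identified and examined separately without a new sample. The analysis is descriptive, so no formal test is at risk. Sampling continues in later weeks, when the residue has largely gone.

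Most of this stands, and it limits the size of the point. It does not supply the missing measurement. Identifying an infant as exposed does not say how much drug was present. A modeller could estimate a non-zero starting amount, but the first sample comes after dosing, the protocol itself calls absorption kinetics poorly defined, section 6.9 does not list the time of the mother's last dose, and there are ten infants. Such a baseline would be weakly identified.

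A reader might infer that the model starts at zero concentration, or that maternal drug is counted as study-drug exposure. The protocol does not support either. Section 7.1 is silent on initial conditions and refers to established models that are not shown, and an analysis plan may deal with the matter.

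A reader might also take C0 / (C0 + 0.5), which is 9% to 44% for the assumed residuals, as the bias. That ratio refers to time zero, when study drug has not yet reached 0.5 ng/mL and no sample is taken. It does not measure bias in exposure or clearance.

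**Conclusion.** The point holds as a design gap. Infants of mothers on buprenorphine are eligible, the primary analyte is the drug they may already carry, and no sample before the first dose is scheduled for assay.

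Under the stated assumptions the residue is about 2% to one third of the concentration at 24 h and about 1% to 19% of week-1 AUC, in affected infants only. It is at most about 3% of the concentration by the end of week 1. Whether that is negligible or material depends on residual level, half-life and number of affected infants, none of which the protocol gives. Confidence is high that the gap exists and low about its size.

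The finding does not show that the primary result will be biased or that the full exposure profile is compromised. It is a cheap improvement to the primary endpoint.

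**What to change.** **Table 9.** Add one sample before the first dose, assayed for buprenorphine and norbuprenorphine, at least in infants with maternal buprenorphine exposure.

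**Source of the blood.** Use plasma from the pharmacogenetic tube of section 6.14 when it is drawn before therapy and its volume suffices. Otherwise use a clinically indicated pre-treatment draw of up to 0.4 mL. Added blood cannot be ruled out: section 6.14 permits 0.2 mL, half the PK goal volume, as well as later collection or a swab. Section 6.14 names lithium heparin, whereas Appendix 3 names an uncoated tube for DNA with anticoagulant as an option; the two should be reconciled.

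**Analysis.** In section 7.1 or the analysis plan, enter the measured values as the baseline for parent and metabolite, and add a sensitivity fit without the maternal-buprenorphine infants.

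**Cost.** One table row, one more assay per infant and possibly 0.4 mL of blood, within the 12 mL limit. Where the tube is shared, DNA must come from the spun cells. A single baseline sample does not capture any continuing intake through breast milk; the recorded "daily intake (cc/kg/day) and type of feed" can only describe who might be affected.

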## 6.11 Efficacy

Length of treatment and length of stay will be collected in units of days. A day is defined as calendar day (rather than 24 hour blocks).

## 6.12 Safety

The safety and tolerability of sublingual buprenorphine will be evaluated by tabulating adverse events. Summary statistics will be used to describe relative rates in major organ systems.

## 6.13 Urine Samples for Metabolite Analysis

Urine collections will take place while on treatment every 5-7 days (or within on day of treatment cessation). Urine will be collected by means of absorbent cotton balls in the diaper. These will be squeezed into collection tubes. A description of urine processing is outlined in Appendix 3. Due to the difficulty of reliably collecting urines from infants, and the role of this assessment as an exploratory goal, failure to collect urine will not be considered a protocol deviation or violation.

## 6.14 Blood Samples for Pharmacogenomics

A single 0.2-0.4 ml whole blood sample is collected in a lithium heparin tube. This sample will be collected prior to the initiation of therapy. If this is not possible, the sample can be collected at any time post randomization. Wherever possible, pharmacogenetic samples will be paired with a standard of care blood draw. A description of blood processing is outlined in Appendix 3. Alternatively, DNA can be obtained through the use of a cheek swab.

## 7 STATISTICAL/ANALYTICAL METHODS AND POWER ANALYSIS

### 7.1 Pharmacometrics

The population PK/PD data will be analyzed using nonlinear mixed-effect modeling with the NONMEM software system (Version VI, Level 1.1, GlobalMax LLC, Hanover, MD, USA) with the PREDPP model library and NMTRAN subroutines. Sparse datasets for buprenorphine will also be analyzed using advanced modeling software (metrumrg package on RStudio, [www.R-project.org](http://www.R-project.org)) to better support modeling and simulation efforts. Based on established population PK models, parent-metabolite relationship will be used to further understand buprenorphine disposition characteristics and inter-individual and residual variability in the study population. Model selection criteria will be based on diagnostic plots (predicted versus observed concentrations, residuals versus predicted concentrations, weighted residual versus predicted concentrations), reasonable parameter estimates, precision of the parameter estimates, random residual variances, and objective function values. To discriminate between competing models, a decrease in the OFV > 10.83 will be considered significant ( $p < 0.001$ ).

Developmental changes in newborns with NAS will be evaluated using NONMEM and SIMCYP (Version 8.1, SIMCYP Inc, Sheffield, UK). Simulation will be performed based on the best model selected which provides accurate and precise estimates of inter-subject variability and the mean parameter values. The simulation would provide initial dose strategy for drug treatment and allow Bayesian feedback analysis for dose individualization.

### 7.2 Power Analysis

No formal power analysis is performed. This analysis is primarily descriptive and will build upon existing buprenorphine neonatal models.

### 7.3 Efficacy, Safety and Pharmacogenetics

Efficacy, safety, and pharmacogenetic analysis are expected to be exploratory and descriptive. There will be no power analysis for these endpoints. Pharmacogenetic analysis will primarily be to correlate externally identified variants which may impact buprenorphine pharmacokinetic disposition. Pharmacogenetic analysis may also assist in assessing the biologic basis for extreme outliers of buprenorphine concentration.

## 8 SAFETY PARAMETERS

There are anticipated to be few mechanism-based risks specific to opioid treatment outside of theoretical

risks of respiratory depression or excessive sedation. A symptom-driven dose titration serves to minimize risks of over-, or under-treatment with opioids. This approach in standard of care treatment of the neonatal abstinence syndrome is very effective in maintaining drug dose within a therapeutic window. All infants will be monitored until stabilization in a high acuity of care setting on 24-hour telemetry monitoring of heart rate and respiratory function. Treatment of other emergent adverse events, whether judged to be drug related or not, will be managed by the neonatology staff of the neonatal intensive care unit (NICU). The NICU has 24-hour senior level physician coverage and access to all subspecialty consultants. The case mix includes a wide spectrum of illness through critical care. The staff is able to manage, jaundice, vomiting, seizures, and infections.

## 8.1 Blood volume

No more than 12 ml of blood will be drawn over the course of the study. This represents a maximum, and not the typical amount drawn. This will include study-related blood draw as well as clinically indicated collection.

Table 10: Blood Volume for Study Participants

Procedure	Research Related?	Total Number of Collections	Blood (mL) per Test	Total Blood (mL/test)
Newborn Hematology/chemistry	No	1	0.8	0.8
PKU screen	No	1	0.4	0.4
Pharmacogenetic sample	Yes	1	0.4	0.4
Buprenorphine assay	Yes	20*	0.4	8.0*
Maximum amount of blood drawn per female patient				10.6*
Circumcision blood loss (estimated)				0.2
Maximum amount of blood drawn per male patient				10.8*

\* maximum

## 8.2 Stopping Rules

No further enrollment will take place following a SAE judged to be probably or definitely related to study treatment. Following a related SAE, the independent safety monitor will review the adverse event and assess investigator designated causality. The safety monitor can request pharmacokinetic analysis for the affected infant if there is concern that the event was exposure related. Depending upon the clinical situation, options could include 1) continuation of study treatment with or without dose adjustment, 2) transition from buprenorphine to open label morphine, 3) transition from an opioid to phenobarbital monotherapy, or 4) cessation of all abstinence pharmacotherapy. This decision will be a consensus approach with the

investigator, with the input of the IRB in case of conflict between investigators and the safety monitor.

If an infant is withdrawn from the study, treatment will follow clinician guidance and will not be protocol-driven. However, such infants will be followed and will be included in safety analysis. There is no prespecified stopping rule for trial cessation. There is no predefined interim look for safety or efficacy.

### **8.3 Data Safety Monitoring Plan**

An independent medical monitor will evaluate each serious adverse event judged by the investigator to be possibly, probably, or definitely related to study drug. The monitor will provide recommendations to the investigators.

### **8.4 Certificate of Confidentiality**

A certificate of confidentiality will be obtained prior to enrollment of any protect to protect privacy of neonates and their mothers.

**APPENDIX 1: NAS SCORING SYSTEM**

Scored Elements	
Signs and Symptoms	Score
Crying: Excessive high pitched	2
Crying: Continuous high pitched	3
Sleeps < 1 hours after feeding	3
Sleeps < 2 hours after feeding	2
Sleeps < 3 hours after feeding	1
Hyperactive Moro Reflex	1
Markedly Hyperactive Moro Reflex	2
Mild Tremors: Disturbed	1
Moderate-Severe Tremors: Disturbed	2
Mild tremors: Undisturbed	1
Moderate-Severe Tremors: Undisturbed	2
Increased Muscle Tone	1-2
Excoriation (Indicate specific area):	1-2
Generalized Seizure (or convulsion)	8
Fever > 37.3 C (99.2 F)	1
Frequent Yawning (4 or more successive times)	1
Sweating	1
Nasal Stuffiness	1
Sneezing (4 or more successive times)	1
Tachypnea (Respiratory Rate >60/mm)	2
Poor feeding	2
Vomiting (or regurgitation)	2
Loose Stools	2
Failure to thrive (Current weight > 10% below birth weight 90% BWT= _____ (record weight in score box 1 x day)	2
Excessive Irritability	1-3
Total Score	
Unscored Elements	
Convulsions	Present/absent
Fever > 38.4 C (101.2 F)	Present/absent
Mottling	Present/absent
Excessive sucking	Present/absent
Watery Stools	Present/absent
Projectile vomiting	Present/absent
Retractions	Present/absent
Nasal flaring	Present/absent
Myoclonic jerks	Present/absent

## APPENDIX 2: PREPARATION OF BUPRENORPHINE STOCK SOLUTION AND STABILITY

	Stability of Stock

Buprenorphine 0.075 mg/mL
 
Composition of neonatal stock solution
 

• One 0.3 mg ampule buprenorphine [Buprenex 0.3 mg/ 1 ml (Reckitt Benckiser) or generic buprenorphine for injection]

• Ethanol to bring to final concentration of 30% (1.26 mL of 95% ethanol USP)

• Simple syrup USP(Sucrose, Purified Water and 0.1% Sodium Benzoate) to bring to 4 mL total volume [Humco or equivalent]

 
0.3 mg buprenorphine per vial * 4 mL  (final volume) = 0.075 mg/mL
	7 days

## **APPENDIX 3: PROCESSING OF PHARMACOKINETIC AND PHARMACOGENETIC SAMPLES**

Buprenorphine and its metabolites are stable in frozen plasma at -20 C for at least 6 months. In urine, there is stability for 16 hours at 22 C, 72 hr at 4 C and through 3 freeze/thaw cycles.

### **Pharmacokinetic Serum Samples**

Samples will be obtained by capillary heel stick into lithium heparin pediatric tubes (BD Microtainer, Ref # 365971 or equivalent). A goal of 400 microliters should be collected. Blood is spun at 3,000 RPM on a refrigerated tabletop centrifuge for 10 minutes, and plasma transferred to storage tubes and frozen at -20 C. Blood from an indwelling catheter can be used if one is present for medical care unrelated to the treatment of NAS.

### **Pharmacokinetic Urine Samples**

Volume of urine will be recorded, as well as time of start and stop of urine collection. Uncentrifuged urine from the collection bag will be transferred to a polypropylene tube and frozen at – 20 C.

### **Blood for DNA**

Blood for DNA analysis will be collected by capillary heel stick into an uncoated capillary pediatric tube. Blood can also be collected in tubes containing anticoagulants.

